10.3 Method of collection of safety information

The DSMP for this study focuses on close monitoring of GWG in conjunction with a safety officer and data and safety monitoring board (DSMB), along with prompt reporting of excessive adverse events and any serious adverse events to the NIH/NHLBI and to the Institutional Review Board (IRB). Because behavioral interventions aimed at preventing excessive GWG could theoretically result in insufficient weight gain by study participants, individual participant weight will be closely monitored by the investigators in conjunction with the participants' primary care providers as described below in detail (see above in section 10.2 for more information). The DSMB will also closely monitor fetal growth, blood and urine findings. Safety reports will be sent to the study statistician, the PIs, and the safety officer quarterly. At least once per year, the DSMB will convene to review study progress and issues related to the safety of the study interventions. Meetings may be more frequent than once per year if the need for such meetings becomes apparent to the safety officer, PIs, IRB, or NIH/NHLBI. The project manager will be responsible for assembling the data and producing these reports in conjunction with the study statistical team, as well as assuring that all parties obtain copies of these reports.

10.4 Frequency of data collection

As described in study design and procedures section, daily weight data will be collected for intervention monitoring. This data will be reviewed by the program leader in weekly face-to-face sessions. Participants who lose weight will be flagged and their data will be sent to the physician

on staff for review. The frequency of data review for this study differs according to the type of data and can be summarized in the following table:

Data type	Frequency of review
Subject accrual (protocol adherence regarding demographics, inclusion/exclusion)	Bi-Yearly
Adverse event rates including X Y Z (examples) analyses	Bi-Yearly
Individual out of range weight gain	Continuous
Discontinued subjects and Stopping rules report	Bi-Yearly

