Subjects will also complete trainings of the Remote Food Photography Method (RFPM) and My Fitness Pal for dietary intake, and the Breezing Device for metabolism. These measures and descriptions are included as uploaded materials. Women will also be sent-home with a waist-mounted activity monitor (i.e., Actigraph) and asked to wear it for the next 7 days, continuously except for showering and at bed time for an accurate assessment of their activity time (activity counts). They will also be asked to wear a wrist-worn activity monitor (e.g., Jawbone Up; looks like a bracelet) and asked to wear this non-stop for the next 7 days and not to take it off (it can be worn during showering and sleep) for a continuous assessment of activity and sleep patterns. The PI, [name], has used this activity monitoring protocol in previous research, including IRB 24174 Active MOMS and our Study 1 protocol (CATS 00000122). There are no risks associated with using activity monitors in pregnancy. Women will then be scheduled for their first intervention session for the following week and they will return their waist-mounted activity monitor to a study staff member. They will wear the wrist-worn monitor for the remainder of the study. They will be given a standard food scale and weight scale (Wi-Fi Fit Bit Aria) to take home for use in the intervention. If participant agrees to participate, they will be asked to weigh themselves daily until delivery. Urine samples will be collected weekly during the prenatal period to assess basal cortisol level as it relates to stress.

R01 and R56: Participants will be asked to collect voided urine overnight, starting from the time participant falls asleep and ending with the last collection being first morning void after waking for the day. We will provide 1 collection container for whole the whole study for storage of all urine. We will also provide a urine collection hat for easy collection. Participants will track time they went to bed, time of any/all collections overnight and time of first morning void.

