6.3 Duration of Participation

Visit A Pre-Intervention Assessment: 120 minutes (can be split into two 60-minute sessions or if participants choose, can be one 120 minute session).

Visit B Intervention Sessions: For those in the intervention group, they will be participating in one 30-min/week education session. Given the adaptive “step-up dosage” nature of this intervention, participation will increase as the dosage increases, *ranging from 1 day per week of 30-min to up to 4-days/week for 150 minutes plus 10-30 min/week of guided instructor feedback.*

Visit C Post-Intervention Assessment: 60 minutes for the interview and 20 minutes for the postpartum survey.

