The study's informed consent document will include information indicating that the study team will communicate with the participant's OBGYN or Primary Care Provider. The study team will ensure that open lines of communication exist with the healthcare provider in addition to the weight monitoring and review. To establish the lines of communication between the study team and the PCPs, upon participant randomization, the participant is required to have a physician consent form completed to "clear her" for study participation. Healthcare providers will also be directly notified about their patient's participation in the study. A brief description of the study will be shared with them as well as a contact number to call the study team should the provider become concerned about insufficient GWG by their patient. Recognizing that weight monitoring is typically performed at all regularly scheduled primary care appointments, we will ask providers for their collaboration in monitoring prenatal weight gain in that we would like to be alerted to any concerns that their patient is demonstrating insufficient weight gain.

During each face to face visit, staff will calculate weight, BMI, and weight change. If the adverse risk for inadequate weight is identified, we will modify treatment (i.e., recommending increased energy intake). The PIs will review weight and applet data at least twice monthly and then contact the healthcare providers and co-investigator, [name] when appropriate after each individual is closely evaluated as described below. For any individual who meets initial screening criteria for weight gain concerns, numerous factors will be considered in determining whether the women's weight gain is problematic and/or related to study interventions. Examples of such factors include nausea, vomiting, and interval illness. If either the healthcare provider or the study investigators believe that it is possible that these growth patterns are a negative result from study participation, the women will be withdrawn from the study.

Co-Investigator, [name], our biostatistician, will include protocol compliance with inclusion and exclusion criteria, participant compliance with the interventions, and adverse events in consultation with the PI [name], Co-I, [name], and study staff ([name], [name]).

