10.8 Suspension of research

As outlined above, we will continuously monitor adverse event rates in all participants. The safety officer, together with the study investigators, will alert the IRB and the NIH if a greater than or equal to 20% adverse event rate potentially due to study interventions should occur in the treatment group or if significant differences between treatment groups occur.

Discontinuing subjects from the study. Any subject with a physician-diagnosed serious adverse event related to the study interventions will be discontinued from the study. Should insufficient weight gain be detected and the cause of this weight gain is potentially related to the study interventions as determined by the PIs after consultation with the participant's primary care provider, the participant will be discontinued from the study. Other non-minor concurrent illnesses or major changes in the family social environment would also lead to discontinuation as determined by the investigators alone or in consultation with the PCP.

If a woman experiences a contraindication to exercise in pregnancy that precludes her continued participation, she will be discontinued from the study. These are: Hemodynamically significant heart disease, Restrictive lung disease, Incompetent cervix/cerclage, Persistent second [or third] trimester bleeding, Placenta previa after 26 weeks of gestation, Premature labor during the current pregnancy, Ruptured membranes, Preeclampsia/pregnancy-induced hypertension] per the ACOG guidelines [(2015, December). ACOG Committee opinion. Number 650: Physical Activity and Exercise During Pregnancy and the Postpartum Period. *Obstetrics and Gynecology*, 126,(6), 135-142].

If she experiences a warning sign to continuing exercise (moderate to severe dizziness, nausea, headache, abdominal pain/pressure, cramping or contractions, chest pain, calf pain or swelling, fluid leakage, unusual change in fetal movement; see our protocol for unexpected or AE), she will discontinue or stop exercising, immediately.

Criteria for stopping the trial. It is exceedingly unlikely that any new, outside information will become available during this trial that would necessitate stopping the trial. There are two situations, however, that could potentially necessitate stopping the trial: 1) poor recruitment and/or retention and 2) disparate serious adverse events related to GWG.

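### Section 10.4 places the weight review in weekly sessions described only for the intervention arm and gives controls no equivalent procedure, so the between-arm adverse-event criteria in Section 10.8 are at risk of ascertainment bias

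*Combined protocol and SAP*

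**What the plan says.** **Home weights.** Section 6.2 gives participants a Wi-Fi scale, and "they will be asked to weigh themselves daily until delivery". Appendix A says the weights upload wirelessly, so no visit is needed.

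**Session-based review.** Section 10.4 says that "daily weight data will be collected for intervention monitoring" and then that "This data will be reviewed by the program leader in weekly face-to-face sessions". The flag rule follows at once: "Participants who lose weight will be flagged and their data will be sent to the physician" on staff. Section 10.2 adds a second check: "During each face to face visit, staff will calculate weight, BMI, and weight change". Section 6.3 describes the weekly session for one arm: "For those in the intervention group, they will be participating in one 30-min/week education session". Appendix C lists 26 lessons, in gestational weeks 9 to 34. Symptoms and perceived exertion are recorded at five time points in each exercise session (Section 6.2), and Section 11.0 routes warning signs to the adverse-event log.

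**Review not tied to a session.** Section 10.2 also provides for daily weight monitoring with a weekly look at gestational weight gain (GWG), states that "The PIs will review weight and applet data at least twice monthly", and asks providers to raise concerns. The table in 10.4 lists out-of-range gain as reviewed continuously. None of these is restricted by arm.

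**Use of the data.** Section 10.8 monitors adverse-event rates in everyone. The IRB and NIH are alerted if a rate of at least 20% potentially due to the intervention occurs "in the treatment group or if significant differences between treatment groups occur". Disparate serious events related to GWG are one of two listed grounds for stopping the trial. Section 10.7 names descriptive statistics only.

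**The concern.** Insufficient weight gain is the harm on which the safety plan is centred. Section 10.2 recognises that nausea, vomiting or intercurrent illness can also cause it, and the control arm is the natural yardstick for that background. The yardstick works only if both arms are watched equally hard. Followed as written, the plan gives intervention women a weekly in-person weight review plus exercise-session checks. For controls it names no one to carry out the daily, weekly or continuous review. An excess of events in the intervention arm could then reflect closer observation, and a control woman losing weight could be flagged later than an intervention woman with the same loss.

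**Working it through.** **1. The plan's own figure.** Section 8.1 needs 12 per group and allows for 20% dropout: 12 / (1 − 0.20) = 15 per group, 30 in total. This reproduces. The documents give no adverse-event rate, detection probability, test or significance level for the 10.8 comparison, so step 4 rests on assumptions and is shown over a range.

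**2. Who is covered by which route.**

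| Route | Section | Arm | Named reviewer and interval? |
|---|---|---|---|
| Program leader, weekly session | 10.4, 6.3 | Described for intervention only | Yes |
| Weight change at each face-to-face visit | 10.2 | Follows attendance | Staff, each visit |
| Exercise-session symptom checks | 6.2, 11.0 | Intervention only | Yes |
| Daily monitoring, weekly GWG examination | 10.2 | Not limited | Interval only |
| PI review, at least twice monthly | 10.2 | Not limited | Yes |
| Provider alerts | 10.2 | Not limited | Provider, no interval |
| Continuous review of out-of-range gain | 10.4 | Not limited | No reviewer |

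The PI review is the only session-independent study-team check with both a named reviewer and an interval.

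**3. Possible delay for a control woman.** With reviews every d days and onset equally likely on any day, the delay is at most d and on average d/2.

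- Weekly: at most 7 days, average 3.5.
- Twice monthly: 365.25 / 24 = 15.2 days at most, average 7.6.
- Difference: 15.2 − 7 = about 8 days at most, and 7.6 − 3.5 = about 4 days on average.
- If the weekly GWG examination in 10.2 covers controls, the difference is zero.

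**4. Effect on the between-arm comparison.** Assume the same true rate p in both arms, detection of 1 in the intervention arm and s in control. The expected spurious difference is p − p·s = p(1 − s). The chance of a false signal is the sum, over all pairs of counts with two-sided Fisher p < 0.05, of Binomial(n, p) × Binomial(n, p·s). At p = 0.20:

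| s | Spurious difference | Fisher p < 0.05, n = 15 | n = 12 |
|---|---|---|---|
| 1 | 0 points | 1.7% | 1.2% |
| 0.75 | 5 points | 2.1% | 1.4% |
| 0.50 | 10 points | 4.1% | 2.2% |
| 0.25 | 15 points | 8.3% | 4.1% |
| 0 | 20 points | 16.4% | 7.3% |

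At p = 0.10 the false-signal chance stays at or below 1.3% throughout. At p = 0.30 with n = 15 it is 1.7%, 2.9%, 7.8%, 20.4% and 48.5% for the same values of s. When controls show no events, at least 5 intervention events are needed for p < 0.05 at either n.

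**5. Raw imbalance.** Because 10.7 is descriptive, reviewers will see counts. Suppose p = 0.20 with detection of 90% and 50%, so observed rates of 0.18 and 0.10, with 15 per arm. The intervention arm then shows more events 64% of the time and control 18%. With 90% detection in both, each arm is higher about 40% of the time. Fisher p < 0.05 occurs in 2.8% and 1.6% respectively.

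**6. The 20% trigger.** It needs 3 of 15 intervention women (3 of 12 after dropout). Control detection does not enter.

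**The case against.** The strongest reply is that the plan already covers controls. Daily monitoring, the weekly GWG examination, continuous review, PI review and provider alerts carry no arm restriction, and the flag rule in 10.4 speaks of participants in general. This stands against two stronger readings that a reader might infer.

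- **That control weight loss would go undetected.** The arm-neutral routes contradict this. A loss that later rebounds also stays visible in the stored daily series; infrequent review delays the finding but does not erase it.
- **That the comparison is biased as a matter of fact.** Direction and size depend on control detection, which the documents do not give.

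Controls may also be seen weekly. Section 6.2 has weekly urine samples brought to a study visit, and Appendix B lists a weekly session weight on the standardized scale, neither limited by arm. Section 18.0 pays for only three visits, but that concerns the added, non-randomised normal-weight controls. The text between 10.4 and 10.6 was not available for this review, and 10.1 defers to a separate adverse-event protocol. Either may name a control procedure.

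Formal false alarms are uncommon in most of the range above, and Section 8.2 urges caution with any test. Exercise symptoms partly reflect exposure to exercise rather than closer watching.

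What remains is that the only weight review 10.4 describes in operational terms is the session, and the daily weights are said there to be for intervention monitoring. The arm-neutral statements do not say who reviews control weights weekly or how. Nothing in the text read provides for like-for-like ascertainment before arms are compared.

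**Conclusion.** The between-arm criteria in 10.8 are at risk of ascertainment bias. If the twice-monthly PI review is the backstop, a control woman's weight loss may be flagged about 4 days later on average and about 8 at most; if the weekly examination in 10.2 covers controls, there is no delay. At an assumed 20% true rate, full intervention-arm detection and 15 per arm, control detection between 100% and 25% gives a spurious difference of 0 to 15 points and a Fisher signal in 1.7% to 8.3% of trials. Only the between-arm alert and the stopping ground based on disparate events are affected. It would be wrong to extend this to the treatment-arm trigger of 20% or more, which uses no control data. The point merits a change because the comparison bears on the plan's main safety question and the remedy is cheap.

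**What to change.** - **Section 10.4:** run the protocol's existing weight flags every week on the uploaded Aria weights of all randomised women, with one procedure and one reviewer for both arms. State whether randomised controls have weekly contact.
- **Surveys:** add the same short set of adverse-event questions for both arms to the existing monthly surveys.
- **Section 10.8:** base the between-arm comparison on all sources common to both arms: these flags and questions, provider alerts, medical records and ultrasound reviews. Report events found only in intervention sessions (face-to-face checks, exercise symptoms) separately for that arm.

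The cost is one script on data already collected, one short survey form and some wording in the safety plan. No clinical threshold changes. The small downside is more control-arm flags for the physician to review.

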10.6 Frequency of review of cumulative data

The frequency of cumulative data review for this study is outlined above and will occur yearly or more frequently as determined by the data safety monitoring committee.

10.7 Statistical tests

Descriptive frequencies, means, and trajectories for weight and GWG.

10.8 Suspension of research

As outlined above, we will continuously monitor adverse event rates in all participants. The safety officer, together with the study investigators, will alert the IRB and the NIH if a greater than or equal to 20% adverse event rate potentially due to study interventions should occur in the treatment group or if significant differences between treatment groups occur.

Discontinuing subjects from the study. Any subject with a physician-diagnosed serious adverse event related to the study interventions will be discontinued from the study. Should insufficient weight gain be detected and the cause of this weight gain is potentially related to the study interventions as determined by the PIs after consultation with the participant's primary care provider, the participant will be discontinued from the study. Other non-minor concurrent illnesses or major changes in the family social environment would also lead to discontinuation as determined by the investigators alone or in consultation with the PCP.

If a woman experiences a contraindication to exercise in pregnancy that precludes her continued participation, she will be discontinued from the study. These are: Hemodynamically significant heart disease, Restrictive lung disease, Incompetent cervix/cerclage, Persistent second [or third] trimester bleeding, Placenta previa after 26 weeks of gestation, Premature labor during the current pregnancy, Ruptured membranes, Preeclampsia/pregnancy-induced hypertension] per the ACOG guidelines [(2015, December). ACOG Committee opinion. Number 650: Physical Activity and Exercise During Pregnancy and the Postpartum Period. *Obstetrics and Gynecology*, 126,(6), 135-142].

If she experiences a warning sign to continuing exercise (moderate to severe dizziness, nausea, headache, abdominal pain/pressure, cramping or contractions, chest pain, calf pain or swelling, fluid leakage, unusual change in fetal movement; see our protocol for unexpected or AE), she will discontinue or stop exercising, immediately.

Criteria for stopping the trial. It is exceedingly unlikely that any new, outside information will become available during this trial that would necessitate stopping the trial. There are two situations, however, that could potentially necessitate stopping the trial: 1) poor recruitment and/or retention and 2) disparate serious adverse events related to GWG.

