1.2 Primary Study Endpoints

Gestational Weight Gain [GWG] – amount of weight gained over the course of the total pregnancy as well as in smaller time points such as weekly, monthly, and in the pregnancy trimesters and weight behaviors

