1.3 Secondary Study Endpoints

Healthy eating [HE] and physical activity [PA] behaviors

Self-regulation behaviors

Sleep behaviors

Adult temperament

Psychological well-being (body image satisfaction, depressive symptoms, anxiety, perceived and actual stress)

Motivational determinants of HE and PA (attitude, social norm, perceived control, self-efficacy, intention)

Social-demographic and health correlates (e.g., age, pregnancy history, etc.)

Fetal growth, weight, height, birth weight, postnatal weight

Mobile resting metabolic rate, basal metabolic rate, metabolism

R56:

C-reactive protein/micronutrients (e.g., folate)

Maternal and infant labor and delivery complications

Maternal/Fetal hydration

Maternal/Fetal medical record data

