3.3 Early Withdrawal of Subjects

3.3.1 Criteria for removal from study

Safety reasons (develops a contraindication to exercise in pregnancy right after recruitment that would exclude her participation from the study; develops a fetal abnormality that requires her to withdrawal from the study per her provider's recommendation)

Failure of subject to adhere to protocol requirements (e.g., not completing assessments and intervention sessions)

Subject withdrawals from study

No returned contact from the subject after recruitment

Pregnancy loss [e.g., miscarriage after recruitment]

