3.3.2 Follow-up for withdrawn subjects

Subjects will be withdrawn from the study based on the criteria listed above. We will make multiple attempts to contact the subjects who fail to return contact after recruitment [our general protocol is to call and email 3 times over a 2-week period, send 1 post card reminder the following week, make 1 additional call and if no contact, the subject is removed from the study] and her data will be coded as loss to follow-up. If a woman is removed for safety reasons, failure to adhere to protocol requirements, or withdraws from the study on her own, we will ask if we are able to continue to follow-up with her for the post-intervention assessments she is willing to complete. If the answer is NO, we will not contact the subject and keep the data that we have collected which will be coded as no follow-up. If the answer is YES, we will maintain protocol contact as applicable (e.g., email/phone) and obtain the appropriate follow-up measures (e.g., completing surveys) and these data will be coded as withdrawal-follow-up.

Subjects will be replaced in study 2 (randomized) according to the randomization scheme. Co-I, [name], HMC, is in charge of the randomization scheme.

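### Section 10.8 ends study participation, not only exercise, for listed pregnancy complications, so later scans, home weights, urine and infant measures can be lost for reasons linked to the endpoints

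*Combined protocol and SAP*

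**What the plan says.** Section 10.8, under discontinuing subjects, states: "If a woman experiences a contraindication to exercise in pregnancy that precludes her continued participation, she will be discontinued from the study". The next sentence spells out the conditions meant. They include "Premature labor during the current pregnancy, Ruptured membranes, Preeclampsia/pregnancy-induced hypertension", as well as placenta previa after 26 weeks and persistent bleeding. The paragraph names no arm and sets no time limit. The paragraph after it treats warning signs during exercise differently: there the woman stops exercising, and nothing is said about leaving the study.

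Section 3.3.1 gives a parallel removal reason, a woman who "develops a contraindication to exercise in pregnancy right after recruitment that would exclude her participation from the study".

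Section 3.3.2 covers what follows. For a woman removed for safety, "we will ask if we are able to continue to follow-up with her for the post-intervention assessments she is willing to complete". If she agrees, contact is kept and suitable measures are collected, with surveys as the only example. If she declines, she is not contacted again, but data already collected are kept. Withdrawn randomised subjects are replaced.

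The primary endpoint in Section 1.2 is gestational weight gain (GWG), including the "amount of weight gained over the course of the total pregnancy". Secondary endpoints in Section 1.3 include "Fetal growth, weight, height, birth weight, postnatal weight" and "Maternal and infant labor and delivery complications".

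**The concern.** A contraindication to exercise is a reason concerning exercise, but the stated consequence is leaving the study. Three things follow.

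- **The trigger is tied to the endpoints.** Premature labor, ruptured membranes and hypertensive disease are themselves pregnancy complications, and they bear on fetal growth and birth weight, which Aim 2 compares between arms. If measurement stops when such an event occurs, the missing data depend on the outcome under study.
- **The rule is not confined to women who exercise.** Section 3.1 gives the normal-weight controls the same measurements and no intervention, and Section 6.3 describes sessions only for the intervention group. For these women the stated reason does not explain why weighing or scanning should end.
- **The analysis plan has no answer to this kind of loss.** Section 8.2 compares the characteristics of women with and without missing data. It gives no sensitivity analysis and no handling of such events. Its mixed models use daily and weekly data, which is where the gaps would fall. Replacement fills the place with another pregnancy and does not recover the affected one.

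The study is meant to supply estimates for a future trial and data for fetal-growth models, so truncated series from the affected pregnancies would matter to both uses.

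**Working it through.** **Inputs**

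- 12 evaluable per group, 20% drop-out, 30 recruited: Section 8.1.
- Entry at 6 to 16 weeks: Section 3.1.
- Scans from 13–15 weeks, then every 5 weeks, at most six: Section 6.2.1.
- Proportion developing a listed condition after entry, q: not given in the documents. Assumed range 5% to 25%.

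**1. The plan's own figure.** 12 / (1 − 0.20) = 15 per group, and 2 × 15 = 30, which reproduces. The allowance is 30 − 2 × 12 = 6 women, the same 6 as in Section 15.0.

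**2. Timing: Section 3.3.1 against Section 10.8.** Section 3.3.1 limits the removal to just after recruitment. Section 10.8 has no limit, and its list contains a condition defined only after 26 weeks. The latest entry is 16 weeks, so that condition arises at least 26 − 16 = 10 weeks after eligibility ends. Staff cannot follow both passages as written.

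**3. What survives removal.**

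| Data | Source in the plan | After removal under 10.8 |
|---|---|---|
| Complications, delivery data, clinic-recorded GWG | Medical records with authorization (6.2.1, Appendix A) | Not stated to stop; the woman may refuse access |
| Week-35 follow-up assessment (Visit C) | 6.2.1, Appendix C | Offered under 3.3.2 if willing |
| Five-weekly scans | 6.2.1 | Not addressed |
| Daily home weights, weekly urine | 6.2.1, Appendices A and B | Not addressed |
| Infant body composition, 6–8 weeks | Visit D in 6.2.1 | Not addressed by name |

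**4. Effect on the scan series.** The schedule gives scans at about 13–15, 18–20, 23–25, 28–30, 33–35 and 38–40 weeks. As an illustration, a woman removed at week 32 would miss the last two of six. A later event costs less.

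**5. Size under the assumed range.** Expected number affected = 30 × q. Chance of at least one in an arm of 15 = 1 − (1 − q)^15. If every such woman were lost to a measure independently of, and on top of, the planned 20%, the number per arm would be 15 × 0.80 × (1 − q).

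| q | Affected of 30 | At least one per arm | Left per arm (12 planned) |
|---|---|---|---|
| 5% | 1.5 | 0.537 | 11.4 |
| 10% | 3.0 | 0.794 | 10.8 |
| 15% | 4.5 | 0.913 | 10.2 |
| 20% | 6.0 | 0.965 | 9.6 |
| 25% | 7.5 | 0.987 | 9.0 |

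The last column is an upper bound on the loss and applies only to measures that stop. If these women fall within the 20% allowance, 12 per arm are kept, but the loss still depends on the outcome. If they are followed, 15 per arm remains enough.

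**The case against.** A reader might infer that these women leave before the endpoints are measured, that complication rates and late GWG are lost, or that the observed complication rate must be zero. The documents do not support this. The protocol takes GWG, complications and labor and delivery data from medical records, and nothing ends that access at discontinuation. The condition that triggers removal is known at that moment, collected data are kept, and Section 8.2 defines no completers-only analysis. A zero rate appears only if one chooses to look solely at women who stayed.

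Other points on that side:

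- **The wording carries a qualifier.** Section 10.8 speaks of a contraindication that rules out continuing. This counts for something, but the following sentence equates it with the whole list.
- **Coverage of both arms is inferred from silence.** That is correct. It is the literal reading, not an express statement. The normal-weight controls are not randomised, so losing them could not bias the randomised comparison.
- **Section 3.3.2 is more generous than it looks.** Surveys are an example, not a limit, and contact is maintained where she agrees. It remains true that the offer concerns post-intervention assessments and that serial scans, home weights and urine are not named.
- **This is a pilot.** Section 8.2 disclaims definitive claims, and Aim 2 is partly exploratory. That lowers the stakes, but a feasibility study should still test the follow-up procedures it intends to carry forward.

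It would also be wrong to set losses among all 50 women, including the 20 additional controls, against the allowance of 6, which belongs to the 30 randomised women.

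**Conclusion.** The point stands in a limited form. Section 10.8 makes leaving the study the consequence of conditions tied to the secondary endpoints, names no arm, and conflicts with Section 3.3.1 on timing. Follow-up under Section 3.3.2 is voluntary and leaves unspecified the later scans, home weights, urine and infant measurement. Those are the data at risk. Record-based GWG, complications and delivery data are largely protected if the woman authorizes access.

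At an assumed 5% to 25%, 1.5 to 7.5 of the 30 randomised women would be affected, against a total allowance of 6. That range is an assumption with no basis in the documents, and the actual data loss depends on when events occur and how many women accept follow-up. The conflict on timing and the failure to separate exercise from study participation do not depend on it. The change should be made, although the study is not undermined without it.

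**What to change.** 1. Reconcile Sections 3.3.1, 3.3.2 and 10.8 on when this removal applies and to whom, and cross-refer 10.8 to 3.3.2.
2. Separate stopping intervention components from stopping outcome data collection.
3. State which already planned measures continue in both arms after such an event: chart abstraction under the authorization, and scans, home weights and infant measures where the woman consents and her provider does not object. Say whether weekly urine is among them.
4. Record the event with its date and arm, and say in Section 8.2 how affected women are analysed.

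Whether and when exercise or participation stops on clinical grounds is for the investigators, and no rule is proposed here.

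The cost is wording in a few sections. No new procedure is needed, because every measure is already scheduled. Some scans or weighings will still be missed when a woman is unwell.
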